6.3 Demographic and Baseline Variables

Summary tables and/or listings will be provided for demographics and other baseline characteristics, including

- Primary tumour origin
- Prior medical treatment
- Tumour grade, KI-67 and KPS/ECOG (reclassified: ECOG 1=KPS 70 or 80 and ECOG 0=KPS 90 or 100)
- Age, ethnic origin, sex, physical exam
- Medical/surgical history at baseline,
- Prior and concomitant medication
- Time from primary diagnosis, time from diagnosis of progression, number and type of prior therapies for condition
- Histological entity, functional state
- HRQL scores at baseline (QLQ C30 and GI.NET21 questionnaires)

For all variables of the population characteristics, p values will be derived by using non-parametric statistical tests to compare both treatments at baseline on a purely descriptive level (“homogeneity tests”; except for detailed physical exam, medical/surgical history and prior/concomitant medication).

6.4 Concomitant Diseases and Medical Conditions

MedDRA coding for this study will be started with version 19.1 or 20.0, based on the time of the first AE, and updated with every MedDRA release. The following data will be coded:

- Adverse Events
- Medical History
- Surgical History

These data will be summarised in tables and listings as described in section 11.

The Preferred Term (PT) and System Organ Class (SOC) for each coded item will be populated in the clinical database, but entire term hierarchy will be included in the exported data to the Biostatistician unless otherwise requested.

6.5 Prior and Concomitant Medication

ATC Hierarchy will be used for coding of the following data:

- Concomitant medication
- Previous Therapy
- Somatostatin Analogues Medication
- Post Study Follow-up Treatment Received

Prior medication is defined as medication taken up to 4 weeks prior to the screening visit.

Concomitant medication is defined as medication taken from baseline until EOS (including herbal products).

6.6 Treatment Compliance and Extent of Exposure

The following variables will be analysed:

- ¹⁷⁷Lu-edotreotide arm:
 - ¹⁷⁷Lu-edotreotide infusion, amount of activity injected compared to per protocol
 - Injection schedule (number of doses, mean treatment duration and mean dose interval for each of the 3 dose intervals: D1 to D2, D2 to D3 and D3 to D4), compared to per protocol schedule.
 - DMTs and treatment discontinuation: count and reasons
- Everolimus arm:
 - Average daily dose until EOS visit (continuous with descriptive stats and $\geq 10\text{mg}$, $[5, 10[$, $< 5\text{mg}$)
 - Mean (and SD) treatment duration
 - DMTs and treatment discontinuation: count and reasons
- By treatment arm and by therapies as:

- Total duration of treatment in month.
- Number of subjects who received SSA as prior and/or concomitant medications
- Subjects with SSA will be also listed

Major protocol deviations with regard to treatment compliance are defined in section 6.2.

6.7 Impact of COVID Infection

In general, any missing visit/assessment window due to COVID will be documented as protocol deviations. Once a subject misses a visit, the subject's impact on the study conduct will be assessed to help distinguish between data "affected" and "unaffected" by COVID. Specific reasons for COVID-related protocol deviations should be provided as detail as possible, including, but not limited to, confirmed/suspected COVID-19 infection, movement restricted due to COVID or social distancing guidelines, drugs shipping delayed/blocked due to COVID, sponsor/site action due to COVID. A listing will be provided to present the COVID-related protocol deviations.

7 Efficacy Analyses

Parameters	Method	Details
Continuous	Summary statistics	number of observations (N), number of missing observations (Nmiss), mean, standard deviation, minimum, 25th percentile, median, 75th percentile, maximum, lower bound 95% confidence interval, upper bound 95% confidence interval
Ordinal and categorical	Frequency counts and percentages	95% confidence interval
Comparison between groups	Van Elteren test (stratified main analysis) and Wilcoxon test (non-stratified sensitivity analysis)	rank-sum
Changes within groups	Wilcoxon test	signed rank
Comparison of percentages	Mantel Haenszel (stratified main analysis) and Fisher's exact test (non-stratified sensitivity analysis)	contingency table

ITM-LET-01	Statistical Analysis Plan
-------------------	----------------------------------

Influence of censored data	Kaplan-Meier analysis and log-rank test (stratified for main analysis and non-stratified for sensitivity analysis)	as appropriate
	Cox proportional hazard regression	for hazard ratio (HR) computation and when adjusting for covariates
	RMST	in case of unequivocal non-proportional hazards or as sensitivity analysis where deemed appropriate
	treating treatment as time-dependent variable and/or RPSFT and/or censoring at time of switch	to account for new anti-cancer treatment starts and treatment switches in the two arms where necessary

All p-values less than 0.05 will be considered “statistically significant” on a descriptive level. p-values resulting from a main confirmatory test for primary and key secondary endpoints will be considered "statistically significant" according to the interim analysis and multiple testing plan (see Section 5.7).

7.1 Primary Efficacy Analysis

Variable	Method	Details
PFS	Kaplan-Meier methods incl median estimates and Log-rank tests (stratified for the main analysis and non-stratified for sensitivity analysis); Cox proportional hazard (for all hazard ratios and multivariate sensitivity analyses)	Take into account the impact of censored observations* For the main analyses, in addition to the 95%CI, the Hazard Ratio Confidence Interval will also be presented adjusted on the analysis level**

*See Section 3.4.1 for more details

** At the first interim analysis the 99.7% CI will be also reported for the HR, at the second interim analysis the 98.2%CI and at the final analysis the 95.6%CI (see Section 5.7 for more details)

In case of unequivocal non-proportional hazards, RMST approach will be used (see Section 6 for more details).

ITM-LET-01	Statistical Analysis Plan
------------	---------------------------

7.2 Key Secondary Efficacy Analysis

Variable	Method	Details
objective response rates (ORR),	Mantel Haenszel test (stratified main analysis) and Fisher's exact test (non-stratified sensitivity analysis)	defined as the proportion of patients achieving partial response (PR) or complete response (CR) as best outcome
Overall survival (OS)	Kaplan-Meier method, Cox models and Log-rank tests as appropriate* (stratified main analysis and non-stratified for sensitivity analysis)	Take into account the impact of censored observations

* In case of a high number of patients in the control arm starting new anticancer treatment or switching to PRRT treatment, appropriate methods to account for new anti-cancer treatment starts and switches in the two arms must be used for the main analysis of OS (see Sections 3.4.2 and 6 for more details).

7.3 Other Secondary Efficacy Analyses

Variable	Method	Details
Percentage of patients progression-free at 2 years after randomisation in either treatment arm (% 2y-PFS)	Estimates based on PFS Kaplan Meier curve	With 95% CI
Disease control rate (DCR)	Mantel Haenszel test (stratified main analysis) and Fisher's exact test (non-stratified sensitivity analysis)	defined as the proportion of patients achieving stable disease (SD), partial response (PR) or complete response (CR) as best outcome
duration of disease control (DDC)	Kaplan-Meier methods incl. log-rank test and median estimates	measured from the time of initial diagnosis of stable disease or better response (SD, PR or CR) until diagnosis of progression
Duration of response (DoR)	Kaplan-Meier methods incl. log-rank test and median estimates	measured from the time of initial diagnosis of response (PR or CR) until diagnosis of progression
Biomarkers and response (see section 3.4.3.1)	Descriptively: subgroups by levels, correlations if relevant, graphs as appropriate	By treatment group

8 Safety Analyses

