#### **9.2.2.2 Exploratory Efficacy Variables**

- c) Percentage of patients progression-free at 2 years after randomisation in either treatment arm (% 2y-PFS)
- d) Disease control rate (DCR), considers – in contrast to the ORR – the percentage of patients, achieving partial response (PR), complete response (CR), and stable disease (SD) as best outcome
- e) Duration of disease control (DDC), will be calculated only in patients who achieve CR, PR or SD as the period from the time point of first establishment of SD (or better) until a new diagnosis of morphological progression per RECIST 1.1 criteria
- f) Similarly, duration of response (DoR), will be calculated only in patients who achieve CR or PR as the period from the time point of first establishment of PR (or better) until a new diagnosis of morphological progression per RECIST 1.1 criteria
- g) Association between RECIST 1.1 tumour response and CgA and/or specific hormone levels will be explored. If relevant, percentage of patients experiencing a biomarker tumour response (CgA, specific hormones), classified as SD, PR, CR, and PD, can be investigated, as well as the duration of such response

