2.2.1 Primary endpoint

The primary endpoint is

- progression-free survival (PFS)

determined as time elapsed between randomisation and the date of first objective report of tumour progression (evaluated by RECIST criteria, 1.1), or death.

For the purpose of the main confirmatory PFS analysis, central blinded image readings in duplicate, with appropriate adjudication in case of discordance will be used. Local assessments will be presented in sensitivity analysis.

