3.4.3 Other Secondary Variables

3.4.3.1 Exploratory Efficacy Parameters

- Percentage of patients progression-free at 2 years after randomisation in either treatment arm (% 2y-PFS)
- Disease control rate (DCR), considers – in contrast to the ORR – the percentage of patients, achieving partial response (PR), complete response (CR), and stable disease (SD)
- Duration of disease control (DDC), will be calculated only in patients who achieve CR, PR or stable disease (SD) as the period from the time point of first establishment of stable disease (or better) until a new diagnosis of morphological progression per RECIST criteria.
- Similarly, duration of response (DoR), will be calculated only in patients who achieve CR or PR as the period from the time point of first establishment of PR (or better) until morphological progression per RECIST 1.1 criteria
- Association between RECIST 1.1 tumour response and CgA and/or specific hormone levels will be explored. If relevant, percentage of patients experiencing a biomarker (CgA, specific hormones) tumour response, classified as SD, PR, CR, or PD can be investigated, as well as the duration of such response

As an example, in patients with an elevated baseline biomarker, changes in biomarker serum concentrations could be classified in analogy to published classifications (Bajetta et al., 1993)

as follows: Complete biomarker response (CR): return to normal range; partial biomarker response (PR): decrease $\geq 50\%$ from baseline, biomarker stable disease (SD): An increase by $< 25\%$ from nadir or decrease by $< 50\%$ from baseline; biomarker progressive disease (PD): increase by $\geq 25\%$ from previous observation nadir.

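### DoR and DDC end at progression only, with no rule for death without progression, and are compared by log-rank in subsets formed after randomisation

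*SAP*

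**What the plan says.** SAP 7.3 gives the end point of both durations. DoR is "measured from the time of initial diagnosis of response (PR or CR) until diagnosis of progression". DDC is "measured from the time of initial diagnosis of stable disease or better response (SD, PR or CR) until diagnosis of progression". The method for each is "Kaplan-Meier methods incl. log-rank test and median estimates".

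The same end point appears elsewhere. SAP 3.4.3.1 takes DoR "as the period from the time point of first establishment of PR (or better) until morphological progression per RECIST 1.1 criteria" and treats DDC alike. Protocol 9.2.2.2 ends both at a new morphological progression. The DDC objective (Protocol Synopsis, Protocol section 2 and SAP 2.1.2) also stops at progression, as do the rollover definitions in SAP 17.7.2.

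The analysis sets are defined by outcome. DoR "will be calculated only in patients who achieve CR or PR" (SAP 3.4.3.1). For DDC, Protocol 9.2.2.2 says it "will be calculated only in patients who achieve CR, PR or SD", and the SAP agrees.

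PFS differs. SAP 2.2.1 ends it at "the date of first objective report of tumour progression (evaluated by RECIST criteria, 1.1), or death". Table 1 in SAP 3.4.1 sets out events and censoring in detail, but is introduced as applying to the main PFS analysis.

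**The concern.** A patient who responds and then dies without documented progression is an event for PFS but has no end event for DoR or DDC. If that patient is censored at death, the Kaplan-Meier estimate treats the response as if it could have continued. The reported median is then longer than the time patients spent alive and in response. If such deaths are more common in one arm, the contrast between arms also shifts.

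The log-rank test raises a separate problem. Membership of the CR/PR or CR/PR/SD subset is decided after randomisation and may be influenced by treatment. Patients who qualify on one arm need not resemble those who qualify on the other, so a difference in duration can appear without any treatment effect on duration, and a real one can be hidden.

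At stake is the interpretation of two exploratory endpoints that are likely to be reported beside ORR. PFS, ORR and OS are not at stake.

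**Working it through.** **No plan figure to reproduce.** The documents give no planning figure for DoR or DDC. The nearest is the PFS power in SAP section 4: 80% with 68 + 112 = 180 events and HR 0.6471. From the event split, power = Phi(|ln HR| x sqrt(d1 d2/(d1+d2)) - 1.96) = Phi(0.4353 x sqrt(68 x 112/180) - 1.96) = Phi(0.4353 x 6.505 - 1.96) = Phi(0.871) = 80.8%. This agrees with the plan, so the same type of formula is used in step 3.

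**Step 1: effect of leaving death out.** Let f be the share of progression-or-death events that are deaths without progression. With constant hazards and such deaths censored, the progression hazard is (1-f) times the total hazard, so

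median (progression only) = median (progression or death) / (1-f).

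| f (assumed) | Factor | 11 months becomes | 22 months becomes |
|---|---|---|---|
| 5% | 1.05 | 11.6 | 23.2 |
| 10% | 1.11 | 12.2 | 24.4 |
| 15% | 1.18 | 12.9 | 25.9 |

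The 11 and 22 months are PFS medians from SAP section 4, used only for scale. A crude ceiling comes from the everolimus planning medians for PFS and OS: 11/44 = 25%, a factor of 1.33. It gives patients still in response or disease control the overall death hazard, so it is probably too high.

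**Step 2: unequal shares by arm.** The progression-only HR is the death-inclusive HR times (1-f_exp)/(1-f_ctl). Taking 0.647 for illustration:
- f = 15% experimental, 5% control: 0.647 x 0.85/0.95 = 0.579
- f = 5% experimental, 15% control: 0.647 x 0.95/0.85 = 0.723

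The shift can go either way.

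**Step 3: size of the DoR comparison.** With the SAP section 4 response rates, responders number 0.18 x 200 = 36 and 0.05 x 100 = 5 (95% binomial ranges 26-47 and 1-10). Even if all 41 have an event, sqrt(41 x 5/41 x 36/41) = 2.095, and:
- HR 0.5: Phi(0.693 x 2.095 - 1.96) = 31% power
- HR 0.647: Phi(0.435 x 2.095 - 1.96) = 15% power
- 80% power needs HR = exp(-2.80/2.095) = 0.26

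**Step 4: what selection can do.** This is a simulation of 4,000 trials of 200 against 100 patients, with no treatment effect on any patient's duration. Better-prognosis patients qualify first, the median duration is 22 months at average prognosis, and follow-up is cut at 24 months. The prognostic spread is the SD on the log-hazard scale. All of these settings are assumptions.

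| Subset | SD 0 | SD 0.5 | SD 1.0 |
|---|---|---|---|
| DDC, control in 90% vs 70% (assumed) | 5.0% | 10.6% | 27.8% |
| DoR, response in 18% vs 5% (planning rates) | 7.1% | 3.1% | 1.9% |

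Entries are rejection rates at two-sided 5%. For DDC the false-positive rate rises with the spread, and the bias runs against the experimental arm. For DoR the drift has the same direction, but with about 5 everolimus responders the test seldom rejects at all.

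**The case against.** **Censoring of deaths is not written down.** This is correct. The SAP is silent on death for these two endpoints. Censoring is the natural reading of a Kaplan-Meier analysis whose only event is progression, but it is an inference. A reader might conclude that the plan overstates durations outright; the documents do not support that. What they show is a missing rule, with a known direction if deaths without progression occur and are censored. In addition, time to progression is itself a legitimate quantity; the medians are long only relative to a progression-or-death definition, the one the SAP uses for PFS.

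**The tests are exploratory.** This also stands. SAP 5.3 calls such tests descriptive, SAP 5.7 keeps everything outside PFS, ORR and OS exploratory, and SAP section 7 applies the descriptive label again. A reader might infer a threat to the trial's type I error; there is none. The label deals with multiplicity, however. It does not tell a reader that these two comparisons condition on a post-randomisation outcome, and section 7 would still call a p-value below 0.05 significant at the descriptive level.

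**DDC is not a responder analysis.** True. It includes stable disease, so the 36-against-5 count applies to DoR only, and selection in DDC weakens as disease control nears 100% in both arms. The size of any DDC selection effect cannot be taken from the documents.

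**Conclusion.** The point holds as a gap in definition and a matter of labelling, with low weight. DoR and DDC end at progression only, no rule covers death without progression, and this differs from PFS in the same SAP. If such deaths occur and are censored, the medians exceed the death-inclusive ones by about 5% to 18% for an assumed share of 5-15% under constant hazards. The share is not in the documents and the true effect could be smaller.

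The log-rank tests compare non-randomised subsets. For DoR the test has little power at the planning rates; for DDC it can mislead if prognosis drives disease control. Neither bears on the PFS, ORR and OS hierarchy.

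**What to change.** - Define DoR and DDC as time from first qualifying response (CR/PR, or SD or better) to progression or death, whichever is first.
- State censoring for new anticancer treatment, missed scans and end of follow-up by adapting SAP Table 1. Where that table falls back to the randomisation date, use the date of first response or first disease control, since these durations start there.
- Report Kaplan-Meier medians with 95% CIs by arm. Drop the log-rank p-values, or label them descriptive comparisons of non-randomised subsets. No replacement test is needed.
- Make the same change in Protocol 9.2.2.2 and in the DDC objective (Protocol Synopsis and section 2, SAP 2.1.2), or record the difference in the SAP, as Protocol 9.3.4 provides for changes in method. Align the rollover definitions in SAP 17.7.2, where no test is planned.

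Cost: wording only. Dates of death are already collected for OS. The medians may become slightly shorter.

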8.1 Adverse Events

Adverse events prior to the first treatment will be captured for all enrolled patients and reported separately from treatment emergent AEs (TEAEs), as baseline findings.

The number of event episode as well as the count and percentage of patients with at least one event will be determined by treatment arm. The analysis will be presented overall and by maximal severity grades.

This analysis will be tabulated for treatment emergent AEs (TEAEs), Adverse reactions (ARs = AEs at least possibly related to the study drug), Serious TEAEs (TESAEs), Serious ARs (SARs), SARs by possible cause of event, TEAEs by action taken on the study drug (change or discontinuation), TEAEs that led to premature study termination, and Fatal TEAEs.

AEs will also be tabulated according to the primary system organ class (SOC), preferred term (PT) and maximal severity. Patient-based count and percentages will be given by treatment arm for SOC followed by those for PT in descending order of the IMP arm.

In this analysis a patient with several events with identical SOC and PT will be counted only once at the maximal severity.

This analysis will be tabulated for TEAEs, ARs, SAEs, SARs, TEAEs by action taken on the study drug (change or discontinuation), TEAEs that led to premature study termination, and fatal TEAEs.

A summary will also be presented by SOC and PT such as mentioned above by treatment arm for all pooled severity grades and pooled grades 3 or 4 TEAEs and ARs.

If deemed appropriate other analysis, table and summaries can be presented to further explore the pattern of adverse events.

All AEs will be listed.

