### ***Intensity/severity***

The intensity of an AE is classified according to NCI-CTCAE version 4.03, taking into account the possible range of the intensity of the event (see Section [8.3.2.3](#)).

- NCI-CTCAE Grade 1 (mild)
- NCI-CTCAE Grade 2 (moderate)
- NCI-CTCAE Grade 3 (severe)
- NCI-CTCAE Grade 4 (life-threatening)
- NCI-CTCAE Grade 5 (fatal)

An AE should be documented with the applicable diagnosis, if possible (rather than as a symptom, sign, or laboratory finding).

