8.2 Deaths, Serious Adverse Events and other Significant Adverse Events

All deaths, AEs and other significant AEs will be listed.

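### The pooled grade 3 or 4 adverse event summary leaves out, term by term, patients whose event was fatal, and no pool of grade 3 or worse is planned

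*SAP*

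**What the plan says.** SAP 8.1 describes three layers of adverse event table.

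- The first gives episodes and patients with at least one event by arm, overall and by highest grade. Its categories include "TEAEs that led to premature study termination, and Fatal TEAEs".
- The second breaks events down by SOC, PT and highest grade. Its counting rule is "In this analysis a patient with several events with identical SOC and PT will be counted only once at the maximal severity". Fatal treatment-emergent adverse events (TEAEs) are tabulated here as well.
- The third is the one at issue: "A summary will also be presented by SOC and PT such as mentioned above by treatment arm", and it is produced "for all pooled severity grades and pooled grades 3 or 4 TEAEs and ARs". ARs are adverse events at least possibly related to study drug.

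Protocol 8.3.2.2 grades intensity on CTCAE version 4.03 with five levels, the fifth being fatal. Grading is done "taking into account the possible range of the intensity of the event". SAP 8.2 adds a listing: "All deaths, AEs and other significant AEs will be listed".

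**The concern.** The second layer assigns each patient one grade per term, the worst one. The third layer then keeps only grades 3 and 4. A severe event that ends in death is grade 5, so it passes out of the top of the pool. For that term, the severe row falls as outcomes get worse, which is the wrong direction for a severity summary.

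Safety and tolerability is a secondary objective, and the frequency and severity of adverse events is a named safety variable (Protocol 9.2.2.3, SAP 3.4.3.2). If severe events under a term are fatal more often in one arm than in the other, that arm's grade 3 or 4 row is lowered more. Only two pools are planned: all grades together, and grades 3 with 4. Neither isolates grade 3 or worse.

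**Working it through.** The plan states no figure on this point, so there is nothing to reproduce. The check is to apply the SAP's own rules to a few artificial records.

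**Inputs**
- Counting rule: one count per patient per SOC and PT, at the highest grade (SAP 8.1).
- Severe pool: grades 3 and 4 (SAP 8.1).
- Scale: grades 1 to 5, with 5 fatal (Protocol 8.3.2.2).
- Inference: an event that ends in death is graded 5, since the grade takes in the range of the event's intensity.

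**Artificial term with four patients.** Highest grades are 3, 4, 5 (a severe event that became fatal) and 2.
- Pool as written, grades 3 and 4: 1 + 1 = 2 patients.
- Pool of grade 3 or higher: 1 + 1 + 1 = 3 patients.
- Sum of the grade 3, 4 and 5 rows of the maximal-severity table for the same term: 3 patients. The missing count can be recovered from a table already planned.

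**Does the order of steps matter?**
- Fatal event held as one record at grade 5: the row shows 2 whether the highest grade is taken first or records are filtered to grades 3 and 4 first.
- Same event held as a grade 3 record and a grade 5 record under one term: taking the highest grade first gives 2; filtering first gives 3. The SAP settles the order only by referring back to the layout described just before.

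**Does the patient leave the whole summary?** Give the fatal case a second term graded 3. That term's row still counts the patient (1). The loss is confined to the term with the fatal event.

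**Size.** For a term with 6 severe cases of which 3 are fatal (assumed), the row shows 6 − 3 = 3.

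Across the trial, the documents give no fatal TEAE rate. Assuming 1% to 5% in each arm and the planned 200 and 100 patients:
- 177Lu-edotreotide: 200 × 0.01 = 2, up to 200 × 0.05 = 10 patients.
- Everolimus: 100 × 0.01 = 1, up to 100 × 0.05 = 5 patients.

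These are upper limits on the patients affected at an assumed rate. They would be spread over many terms.

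**The case against.** The strongest reply is that this is layout, not omission. The maximal-severity table by SOC and PT shows grade 5 with grades 3 and 4, fatal TEAEs are tabulated both overall and by SOC and PT, and all deaths and adverse events are listed. That stands, and it is why the point is minor. It does not correct the pooled row itself, which a reader may take at face value without adding up another table.

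A second reply is that keeping grades 3 and 4 apart from fatal events is a defensible, non-overlapping presentation, and SAP 8.4 pools grades 3 and 4 for laboratory toxicity too. That is fair, provided the row is labelled as excluding fatal events and grade 5 is shown beside it. SAP 8.1 does neither. The table shells are in a separate tracker (SAP 13) that was not available, and they may already do so.

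A third reply is that a wider pool would bring in deaths from progression, which Protocol 8.3.2.5 and 8.3.2.6 treat as serious adverse events even when unrelated to treatment. This stands in part. It is limited because adverse events are collected up to end of study, which for each patient comes no later than progression (Protocol 4.6 and 8.3.2.3). The AR row does not take in deaths judged unrelated.

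A reader might infer that such a patient vanishes from the severe-event summary altogether. The counting rule does not support that: the patient remains under every other term graded 3 or 4.

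**Conclusion.** The point holds as a minor flaw of definition in a descriptive summary. On the natural reading of SAP 8.1, a term's pooled severe row omits patients whose event under that term reached grade 5, and no planned pool isolates grade 3 or worse.

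This rests on two assumptions: that an event ending in death is recorded at grade 5, and that the highest-grade rule carries over to the pooled summary. If a fatal event is held as two records and the grade filter is applied first, the earlier grade 3 or 4 record stays in the row.

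The size cannot be fixed from the documents. The example of 3 shown out of 6 is assumed, as is the 1% to 5% range.

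Two stronger conclusions might be drawn, and neither is supported. One is that this summary is the trial's main toxicity comparison. The SAP introduces it as an additional summary, and no safety test or decision rule uses it. The other is that fatal toxicity would be hidden and one arm made to look safer in the report as a whole. The tables by highest grade and the fatal-event tables would show the deaths by arm directly.

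**What to change.** In SAP 8.1 and the matching table shells, replace the pool of grades 3 or 4 with a pool of grade 3 or higher (3, 4 or 5) for TEAEs and ARs by SOC and PT. Show grade 5 in an adjacent column. State that the pool uses the highest grade per patient and term. Keep the separate fatal TEAE tables.

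The cost is a few words and one extra column, with no new data and no effect on efficacy or alpha. Severe percentages become slightly less favourable. The TEAE row, and to a lesser degree the AR row, may include some deaths linked to progression; the grade 5 column makes these visible.
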